10.2 Randomization

Patients eligible after completing all screening evaluations will be randomly assigned by an interactive response technology (IRT) system in a 1:1 ratio to receive CB-Cabo or Pbo-Cabo.

Randomization will be stratified by the following factors:

- Prior treatment with PD-1/PD-L1 inhibitor therapy: Yes vs. No
- IMDC Prognostic Risk Group: favorable vs. intermediate vs. poor ([Attachment 3](#))

Randomization should occur as close as possible to the planned start of treatment (i.e., within 24 hr if practicable but no more than 3 days). Patients are defined as enrolled in the study if randomized.

Crossover between treatment arms will not be allowed.

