10.3 Study Treatment Procedures

For the complete list of schedules of procedures, please refer to the Schedule of Assessments in [Attachment 1](#).

While the patient is receiving study treatment, the patient's clinical status should be evaluated at each clinic visit to confirm that the patient is suitable for continuing study treatment and to make timely decisions regarding the interruption or restarting of study treatment.

Assessments are based on 28-day cycles. *Radiographic evaluation of tumor burden and QoL questionnaires will be performed as scheduled relative to the date of Cycle 1 Day 1 (C1D1) regardless of study treatment holds or delays.* Additional assessments may occur, as clinically indicated, during unscheduled visits.

After randomization, clinic visits for safety evaluations will occur Day 1 of every cycle (approximately every 4 weeks) for the first 12 cycles. Starting with Cycle 13, safety evaluations will occur every 3 cycles (approximately every 12 weeks). More frequent safety evaluations may be performed if clinically indicated. The final scheduled safety assessment will occur at the End of Treatment Visit. If the study treatment is held due to AEs, Investigators should perform additional safety assessments as clinically indicated.

Radiographic evaluation of tumor burden (e.g., diagnostic computed tomography [CT] scan with intravenous contrast or MRI) will occur during Screening (within 28 days prior to randomization), every 8 weeks after C1D1 for the first 12 cycles, every 12 weeks beginning with Cycle 13, and at the End of Treatment Visit. Radiographic assessments may occur more frequently as clinically indicated.

Quality of life questionnaires will be completed before study drug dosing on C1D1, every 4 weeks after C1D1 for the first 12 cycles, every 12 weeks beginning with Cycle 13, and at the End of Treatment Visit.

Patients who hold or discontinue only one of the study drugs (either CB-839/placebo or cabozantinib) for any reason such as, but not limited to, an AE or surgery, should continue the other study drug on study and continue to have scheduled study visits and procedures per protocol.

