14.6 Efficacy Analysis

14.6.1 Primary Efficacy Endpoint: IRC-Adjudicated PFS

The primary efficacy endpoint is PFS defined as the time from randomization to the earlier of IRC-adjudicated disease progression or death due to any cause. Radiographic disease progression will be assessed using the RECIST v.1.1 criteria. If the disease progression assessment involves more than one date, the earliest date will be used as the event date. The duration of PFS will be censored at the date of the last evaluable radiographic disease assessment prior to the occurrence of any of the following scenarios:

- Patient is alive and progression free at the time of analysis data cutoff

- Disease progression or death occurs after data are missing for two consecutive scheduled radiographic disease assessments, including [a] missing assessments, [b] insufficient data for the assessments, or [c] assessments resulting in a non-evaluable status for overall response per RECIST 1.1.
- Prior to documentation of disease progression or death, patient receives non-protocol anticancer therapy, or any other treatment that in the opinion of the IRC interferes with assessment of disease per RECIST 1.1 (this includes the scenario when the IRC disagrees with the Investigator-judged progressive disease status but the patient received subsequent anticancer therapy).

Patients missing baseline radiographic disease assessment will be censored at the date of randomization (i.e., PFS duration will be 0).

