- ¹¹ Pregnancy testing is required of all females of child-bearing potential. A negative pregnancy test during screening and within 3 days prior to the first dose of study treatment is required. Pregnancy testing on C1D1 is not required if the screening pregnancy test is ≤3 days before the first dose. If a urine test is positive or borderline (unable to confirm as negative), a serum β-hCG test will be required.

- ¹² PK samples are collected on C2D1: pre-dose and 2 hr post dose, and on C3D1: 4 hr and 6 hr post dose. Refer to the laboratory manual for detailed instructions on samples kits, collection, and shipment to a central laboratory. Contact Sponsor for guidance on options for collecting missed samples.
- ¹³ Optional tumor biopsies to be collected as clinically indicated from patients at North American sites only.
- ¹⁴ Screening tumor assessments within 28 days prior to randomization accepted. Radiographic assessments should include brain MRI for patients with history of brain metastases or suggestive symptoms and bone scan (bone scintigraphy) for patients with history of bone metastases or suggestive symptoms.
- ¹⁵ Radiographic tumor assessments and QoL questionnaires will be performed at the scheduled intervals *relative to the date of C1D1* regardless of study treatment holds or delays (note that treatment cycles are fixed and do not shift as a result of dose interruptions).
- ¹⁶ Unless performed within the previous 4 weeks (Note: patients who discontinue study treatment for reasons other than progressive disease [PD] or death will continue to be followed by radiographic tumor imaging until documentation of radiographic PD per RECIST v.1.1, death, initiation of a new anticancer therapy, or withdrawal of consent.)
- ¹⁷ Patients will be contacted every 3 mo for the first 12 mo after discontinuation of all study treatments (CB-839/placebo and cabozantinib) and every 6 mo thereafter for survival follow-up.

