- Lytic bone lesions or mixed lytic-blastic lesions, **with identifiable soft tissue components**, that can be evaluated by cross sectional imaging techniques such as CT or MRI can be considered as measurable lesions if the soft tissue component meets the definition of measurability described above.
- Blastic bone lesions are non-measurable.

Cystic lesions:

- Lesions that meet the criteria for radiographically defined simple cysts should not be considered as malignant lesions (neither measurable nor non-measurable) since they are, by definition, simple cysts.
- ‘Cystic lesions’ thought to represent cystic metastases can be considered as measurable lesions, if they meet the definition of measurability described above. However, if non-cystic lesions are present in the same patient, these are preferred for selection as target lesions.

Lesions with prior local treatment:

- Tumor lesions situated in a previously irradiated area, or in an area patiented to other loco-regional therapy, are usually not considered measurable unless there has been demonstrated progression in the lesion. For this protocol, these tumor lesions will be considered non-measurable lesions.

Specifications by methods of measurements

Measurement of lesions

All measurements should be recorded in metric notation, using calipers if clinically assessed. All baseline evaluations should be performed as close as possible to the treatment start and never more than 4 weeks before the beginning of the treatment.

Method of assessment

The same method of assessment and the same technique should be used to characterize each identified and reported lesion at baseline and during follow-up. Imaging based evaluation should always be done rather than clinical examination unless the lesion(s) being followed cannot be imaged but are assessable by clinical exam.

Clinical lesions: Clinical lesions will only be considered measurable when they are superficial and ≥ 10 mm diameter as assessed using calipers (e.g., skin nodules). For the case of skin lesions, documentation by color photography including a ruler to estimate the size of the lesion is suggested. As noted above, when lesions can be evaluated by both clinical exam and imaging, imaging evaluation should be undertaken since it is more objective and may also be reviewed at the end of the study.

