6.5 Efficacy Analysis

6.5.1 Primary Analysis of Progression-Free Survival

Progression-free survival is defined as the time from randomization to the occurrence of disease progression as assessed by the IRC using RECIST v1.1 or death from any cause, whichever occurs first. Patients who have not experienced disease progression or death at the time of analysis of PFS will be censored at the date of the last evaluable radiographic disease assessment. The duration of primary analysis of PFS will be censored as outlined in Table 4. The sensitivity analysis will be performed if > 5% of patients have a PFS event immediately after missing at least two scans consecutively before the data cutoff, by considering such as event at the first date of documented progression or death.

Treatment comparisons will be based on the stratified log-rank test in the ITT population. The stratification factors will be those used for randomization and will be obtained from the IWRS (prior PD-1/PD-L1 inhibitor therapy [yes vs. no] and IMDC prognostic risk group [favorable vs. intermediate vs. poor]). A 2-sided $p \leq 0.05$ in favor of the CB-Cabo experimental treatment will be regarded as a positive result for the study. The null and alternative hypotheses can be phrased in terms of the survival functions $S_{PFS_CB-Cabo}(t)$ and $S_{PFS_Pbo-Cabo}(t)$ in arm CB-Cabo and arm Pbo-Cabo, respectively:

$$H_0: S_{PFS_CB-Cabo}(t) = S_{PFS_Pbo-Cabo}(t) \text{ versus } H_1: S_{PFS_CB-Cabo}(t) \neq S_{PFS_Pbo-Cabo}(t)$$

Kaplan-Meier methodology will be used to estimate median PFS for each treatment arm and construct survival curves for the visual description of the difference between the treatment arms. The Brookmeyer-Crowley methodology will be used to construct the 95% CI for the median PFS for each treatment arm (1).

The hazard ratio (HR), $\lambda_{PFS_CB-Cabo}/\lambda_{PFS_Pbo-Cabo}$, where $\lambda_{PFS_CB-Cabo}$ and $\lambda_{PFS_Pbo-Cabo}$, represents the hazard of PFS in arm CB-Cabo and arm Pbo-Cabo, respectively. HR will be estimated with a stratified Cox proportional hazards regression model and the same stratification variables used for the stratified log-rank test. In addition, as a sensitivity

analysis for the primary endpoint, the above analyses will be repeated with only two levels, i.e., favorable vs. intermediate/poor, for the IMDC Prognostic Risk grouping.

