To prevent a stratification cell having too few events, if a stratification cell has less than 10 PFS events (two arms combined), the stratification factor that contributes the least number of events for that cell will be removed. Stratification factors for the analyses will be removed until all stratification cells have at least 10 PFS events in two arms combined.

As a sensitivity analysis, the above analyses will be performed using the number of prior TKI cancer therapy (0 vs. ≥ 1) and IMDC prognostic risk group (favorable vs. intermediate vs. poor) and prior PD-1/PD-L1 inhibitor therapy as the stratification factors.

If there is notable imbalance in number of prior lines of anti-cancer therapy between the two treatment arms and if sample size permits, sensitivity analysis will be performed using number of prior lines of anti-cancer therapy (1 vs. 2) and IMDC prognostic risk group (favorable vs. intermediate vs. poor) and prior PD-1/PD-L1 inhibitor therapy as the stratification factors.

Similarly to the primary analysis, to prevent a stratification cell having too few events, if a stratification cell has less than 10 PFS events (two arms combined), the stratification factor of prior PD-1/PD-L1 inhibitor therapy will be removed.

Results from an unstratified analysis will also be provided.

Table 4 Censoring Rules for Progression Free Survival

Situation	Date of PFS Event or Censoring	Outcome
No baseline disease assessment	Date of randomization	Censored
No post-baseline assessments and no death	Date of randomization	Censored
No progression and no death	Date of last evaluable tumor assessment	Censored
Additional cancer therapy prior to documentation of disease progression or death	Date of last evaluable tumor assessment before initiation of additional cancer therapy	Censored
Documented RECIST v1.1 progression or death between scheduled visits [1]	First date of documented progression or death	PFS event
RECIST v1.1 progression or death documented to occur following missing at least 2 consecutive scheduled radiographic disease assessments (including missing assessments, insufficient data for the assessments, and an overall response of non-evaluable) following previous evaluable radiologic tumor assessment	Date of last tumor assessment with no documented progression [2]	Censored [2]

RECIST v1.1, Response Evaluation Criteria in Solid Tumors Version 1.1

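### Patients without a baseline disease assessment are censored at randomization even if they die, against the PFS definition; separately, Attachment 5 dates the baseline scan from a different anchor than the schedule

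*Protocol*

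**What the plan says.** **Censoring.** Protocol Section 14.6.1 states: "Patients missing baseline radiographic disease assessment will be censored at the date of randomization (i.e., PFS duration will be 0". SAP Table 4 repeats this in its first row, "No baseline disease assessment", with the date of randomization and the outcome censored. The second row has the same date and outcome but a narrower trigger: "No post-baseline assessments and no death". SAP Section 6.5.1 defines the endpoint as time from randomization to IRC-assessed progression "or death from any cause, whichever occurs first". Protocol Section 14.6.1 and SAP Section 4.1.1.1 also count any death.

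**Baseline scan window.** Protocol Section 10.3 says that imaging "will occur during Screening (within 28 days prior to randomization". Attachment 1, footnote 14, agrees: "Screening tumor assessments within 28 days prior to randomization accepted". SAP Section 4 repeats the same window. Section 10.2 allows treatment to start after randomization "within 24 hr if practicable but no more than 3 days". Attachment 5, under measurement of lesions, asks for baseline evaluations "never more than 4 weeks before the beginning of the treatment".

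**The concern.** A death can be established without a baseline scan. A rule that censors the patient at time zero whether or not he dies removes an event that the endpoint definition includes, and the patient then contributes nothing to the log-rank comparison although he belongs to the ITT population. Row 2 shows that the authors had this exception in mind for patients without follow-up imaging, so its absence from row 1 looks like an oversight. The same death would count in the OS analysis, so the two endpoints would disagree on whether it occurred.

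The window mismatch is a separate matter of wording. The same scan can satisfy the schedule and breach Attachment 5, and a site or reader has no rule for choosing between them.

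**Working it through.** **1. The plan's own event figure.** Inputs from Protocol Section 14.8: HR 0.69, two-sided alpha 0.05, power 0.85, 1:1 allocation, 416 patients, medians of 8 and 11.6 months, 15 months of accrual plus 7 of follow-up.
- Schoenfeld: d = 4(1.960 + 1.036)² / (ln 0.69)² = 261. With 262 events, power = 0.852.
- Expected events per arm: n[1 − (e^(−λF) − e^(−λ(A+F)))/(λA)], with λ = ln 2/median, n = 208, A = 15, F = 7. The two arms sum to 262.2, or 63.0% of 416.

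The stated 262 is reproduced.

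**2. The censoring rules side by side, for a patient who dies.**
- No baseline (row 1; Protocol 14.6.1): censored at randomization. The time is 0 in the protocol, or 1/30.4375 = 0.03 months by the SAP formula.
- Baseline present, no follow-up scan (row 2): the row does not apply, because it requires no death.
- Endpoint definition: event at the date of death.

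Row 1 therefore disagrees both with the definition and with its neighbour.

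**3. Whether another planned analysis recovers the death.** Footnote [2] of Table 4 and the sensitivity analyses with a 5% trigger (SAP 6.5.1 and 6.5.3.6) concern missed scheduled scans before an event. Investigator-assessed PFS (6.5.2.2) uses the same definition and analysis. The alternative stratifications and the COVID-19 analyses leave row 1 as it is. None clearly restores the event.

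**4. Size.** The documents give no rate of missing baselines, so I assume a share s of the 416 patients. SAP Table 3 estimates 135 deaths at the PFS analysis, or 135/416 = 32.5%. If patients without a baseline die at the same rate, the deaths set aside number at most 135s. The wider figure, 262s, counts every PFS event in those patients, progressions included. Power is by Schoenfeld at 262(1 − s) events, as if the calendar cutoff were fixed.

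| s | Patients | Deaths at most | All events | Power |
|---|---|---|---|---|
| 1% | 4 | 1.4 | 2.6 | 0.848 |
| 2% | 8 | 2.7 | 5.2 | 0.844 |
| 5% | 21 | 6.8 | 13.1 | 0.833 |
| 10% | 42 | 13.5 | 26.2 | 0.813 |

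The cutoff is not fixed. SAP Section 4.3 waits for about 262 events and at least 8 months after the last enrolment, whichever is later. With the SAP's 16 + 8 months, the formula in step 1 gives 276.7 events. Losing 5% leaves 276.7 × 0.95 = 262.9, still at the target. Losing 10% leaves 249.1, and the cutoff would move later.

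**5. Window.** The longest scan-to-dose interval that the schedule accepts is 28 + 3 = 31 days, against 28 in Attachment 5. The conflict covers scans 29 to 31 days before first dose and vanishes when dosing starts on the day of randomization.

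**The case against.** The strongest reply is that row 1 will hardly ever apply. Measurable disease is an inclusion criterion (Protocol 8.1), imaging is required at screening (10.1.2), and eligibility is reviewed before randomization (10.1). This stands, and it is why the point is minor.

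Second, Table 4 already lets censoring override a death, after two missed scans or after new anticancer therapy, so row 1 is not unique. That is true, but those rows rest on something that happened after randomization. Row 1 has no such basis, and row 2, its closest parallel, goes the other way.

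Third, Table 4 also has a row that makes death between scheduled visits an event. A patient without a baseline who dies could fit both rows, and no order of precedence is given. The SAP, which by its Section 3 supersedes the protocol on analyses, is then ambiguous rather than plainly wrong. The protocol sentence is unconditional.

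A reader might also infer that a scan 29 to 31 days before first dose is invalid under Attachment 5 and so sends the patient into row 1. The documents do not support this. Such a scan is neither absent nor missing. Protocol 10.3, Attachment 1 and SAP Section 4 accept it, and SAP Section 6.2 takes the last data before first dose as baseline, with no age limit. Attachment 5 is adapted general RECIST text and attaches no consequence to a late scan. The IRC Charter and Imaging Manual, which may settle how baselines are handled, are not among the documents.

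**Conclusion.** The censoring point holds on its own. For a patient with no baseline assessment, Protocol 14.6.1 and SAP Table 4 row 1 discard a death that the primary endpoint counts, and row 1 is inconsistent with row 2. The expected effect is small: about 1 to 7 deaths at most if 1% to 5% of patients lack a baseline. That range rests on my assumed shares and on these patients dying at the SAP's overall estimated rate. Because the analysis is event-driven, the cost is mainly a few uncounted events and possibly a later cutoff, not a loss of planned power. Treatment is blinded, so there is no evident reason for missing baselines to favour one arm.

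The window mismatch is real but only a matter of reconciliation. It amounts to at most 3 days, and no figure for censored patients can be drawn from it. Nor do the documents say whether row 1 extends to a baseline scan that exists at the site but is unreadable for the IRC.

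**What to change.** - In SAP Table 4 row 1 and the matching sentence of Protocol 14.6.1, add the condition that the patient has not died, as row 2 already does. State that death in a patient without a baseline assessment is a PFS event.
- Keep these deaths under the same limit of two consecutive missed assessments, but give it a start date. The current row counts from a previous evaluable assessment, which these patients lack, so the count should run from randomization. If follow-up scans without a baseline are read as non-evaluable, the second missed scan falls at 2 × 8 = 16 weeks, so the change recovers deaths up to about that time.
- Separately, reconcile Attachment 5 with Protocol 10.3 and Attachment 1 so that one anchor and one limit apply to the baseline scan, and say how the IRC handles a scan outside it.

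The cost is a few sentences in the two documents. The sample size, the 262-event target and the test are unchanged. The censoring change should be made before unblinding.
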